**Table 5-2      Protocol deviation codes and analysis sets (included as reference)**

Category Deviation code	Text description of deviation	Data exclusion
Subjects are excluded from all (safety) analysis in case of these PDs:		Exclude subject completely from all ( safety ) analysis sets
I01	ICF not obtained	Yes
Subjects are excluded from PK analysis in case of these PDs:		Exclude subject from PK analysis set
I01	ICF not obtained	Yes
E07	Deviation from exclusion criterion 7 (V05)	Yes
E11	Deviation from exclusion criterion 11 11(V05)	Yes
Subjects are excluded from Efficacy 1 analysis in case of these PDs:		Exclude subject from Efficacy 1 analysis set
I01	ICF not obtained	Yes

Category Deviation code	Text description of deviation	Data exclusion
E07	Deviation from exclusion criterion 7 (V05)	Yes
E11	Deviation from exclusion criterion 11 11(V05)	Yes
Subjects are excluded from Efficacy 2 analysis in case of these PDs:		Exclude subject from Efficacy 2 analysis set
I01	ICF not obtained	Yes
I02	Deviation from inclusion criterion 2 (V05)	Yes
I03	Deviation from inclusion criterion 3 (V05)	Yes
I04	Deviation from inclusion criterion 4 (V05)	Yes
I10	Deviation from inclusion criterion 4 (V03-04) and 5 (V05)	Yes
E01	Deviation from exclusion criterion 1 (V05)	Yes
E02	Deviation from exclusion criterion 2 (V05)	Yes
E03	Deviation from exclusion criterion 3 (V05)	Yes
E04	Deviation from exclusion criterion 4 (V05)	Yes
E05	Deviation from exclusion criterion 5 (V05)	Yes
E06	Deviation from exclusion criterion 6 (V05)	Yes
E07	Deviation from exclusion criterion 7 (V05)	Yes
E08	Deviation from exclusion criterion 8 (V05)	Yes
E09	Deviation from exclusion criterion 9 (V05)	Yes
E11	Deviation from exclusion criterion 11(V05)	Yes
E12	Deviation from exclusion criterion 12 (V05)	Yes
E13	Deviation from exclusion criterion 13 (V05)	Yes
E14	Deviation from exclusion criterion 14 (V05)	Yes
E15	Deviation from exclusion criterion 15 (V05)	Yes
E16	Deviation from exclusion criterion 16 (V05)	Yes
E17	Deviation from exclusion criterion 17 (V05)	Yes
E20	Deviation from exclusion criterion 20 (V05)	Yes
E21	Deviation from exclusion criterion 21 (V05)	Yes
E22	Deviation from exclusion criterion 22 (V05)	Yes
E24	Deviation from exclusion criterion 24 (V05)	Yes
E25	Deviation from exclusion criterion 25 (V05)	Yes
M01	Use of prohibited medication during the study	Yes

## **6 Statistical methods for Pharmacokinetic (PK) parameters**

Summary statistics for total LFG316 may be analyzed on the PK analysis set.

Summary statistics of total LFG316 concentrations may be provided by visit/time. Summary statistics will include mean (arithmetic and geometric), SD, CV (arithmetic and geometric), median, minimum, maximum, and the frequency (n, %) of concentrations below the LLOQ. A geometric mean will not be reported if the dataset includes zero values.

Total LFG316 concentrations may be expressed as  $\mu\text{g}/\text{mL}$ . All concentrations below the limit of quantification (LLOQ) or missing data may be labeled as such in the concentration data listings. Concentrations below the LLOQ may be treated as zero in summary statistics for concentration data only.

Arithmetic mean (SD) concentration-time plots as well as overlaying individual concentration-time profiles may be provided.

## **7 Statistical methods for Efficacy and Pharmacodynamic (PD) parameters**

### **7.1 Primary endpoint**

The primary endpoints are the response rate (proportion of patients that respond in the study eye) and the remission rate (complete response) at Day 85.

A response will be defined by any one of the following criteria in the study eye:

- An improvement of 2 or more steps in vitreous haze, relative to baseline. For the purpose of “step” calculation, 0.5 shall count as one of the increments. Thus, improvement from a score of 2 to 0.5 or from 1 to 0 would constitute a 2-step improvement or,
- An improvement of 10 or more letters in visual acuity, relative to baseline or,
- An improvement of 2 or more steps in anterior chamber cells, relative to baseline
- Resolution of chorioretinal lesions as determined by the investigator

Remission (complete response) will be defined as

- any patient who has a vitreous haze score of 0 or 0.5 in the study eye, who has an anterior chamber cell score of 0 and no chorioretinal lesions in the study eye and is off all immune modulatory therapy (systemic, corticosteroids and topical), without any worsening of uveitis during the trial.

The analysis of response rate and remission rate at Day 85 will be carried out on the efficacy analysis sets (Efficacy 1 and Efficacy 2), with the analysis on the Efficacy 1 analysis set being of primary interest.

The baseline value will be defined as Day 1 pre-dose value, or the screening values if the Day 1 pre-dose value does not exist.

The response rates and the 90% exact (Clopper-Pearson) confidence intervals in the LFG316 group Corporate Confidential Information will be reported. Corporate Confidential Information

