## 4.2 Exclusion criteria

Patients fulfilling **any** of the following criteria are not eligible for inclusion in this study:

Clinically significant abnormality in screening laboratory results or electrocardiogram (see below for definition on the term "clinically significant").

1. Uveitis that is so severe that, in the investigator's judgment, it is too likely to test an experimental drug.
2. Bilateral uveitis for which, in the opinion of the investigator, systemic immunosuppressive therapy is required to manage the inflammation in the fellow eye; **use of local therapy in the fellow eye is acceptable and not an explicit exclusion** (See [Section 5.5.7](#) for acceptable concomitant treatments).
3. History of retinal detachment
4. In the study eye, cataract expected to interfere with study conduct or require surgery during the study.
5. Pregnant or nursing (lactating) women, where pregnancy is defined as the state of a female after conception and until the termination of gestation, confirmed by a positive hCG laboratory test (>5 mIU/ml).
6. History of hypersensitivity to any monoclonal antibody (mAb).
7. History of infectious uveitis or endophthalmitis in either eye
8. Anticipated need for intraocular surgery during the study period
9. Participation in another interventional clinical study within 12 weeks prior to the start of study treatment.
10. Any medical, psychiatric, or substance-use condition likely to interfere with the patient's participation in the study, or likely to cause serious adverse events during the study.
11. Uveitis with an underlying diagnosis that is uncertain and which would reasonably include a disease for which immunosuppression would be contraindicated (e.g., when the diagnosis of ocular lymphoma, histoplasmosis, toxoplasmosis, etc., are a reasonable possibility) or for which immunosuppression is not proven to be beneficial (e.g., acute zonal occult outer retinopathy, progressive outer retinal necrosis, acute retinal necrosis syndrome, etc.).
12. Forms of uveitis that may spontaneously resolve such as multiple evanescent white dot syndrome (MEWDS).

13. Current use of or likely need for systemic medications known to be toxic to the lens, retina, or optic nerve (e.g., deferoxamine, chloroquine, ethambutol, etc.).
14. Change in low-molecular-weight immunosuppressive medications during the 3 weeks prior to baseline; this does not apply to corticosteroid doses.

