15. Patient is taking corticosteroids or another systemic immunosuppressive medication for any extraocular disease or concurrent medical condition **unrelated** to uveitis (e.g., multiple sclerosis, organ transplantation, moderate or severe asthma, autoimmune disease, etc.) and the tapering or discontinuation of the immunosuppression, including corticosteroids would not be safe because of the risk of exacerbation of the extraocular condition; the patient would be excluded.
16. Any systemic immunosuppressive biologic agent given via intravitreal, intravenous or subcutaneous route such as:
  - Infliximab, daclizumab, etanercept, adalimumab, etc. **within 4** months prior to Day 1
  - Depleting antibodies, e.g., rituximab and alemtuzumab, are excluded for **12 months** prior to Day 1
17. Periocular or intra-vitreal drugs (e.g., corticosteroids) administered to the study eye within three months prior to Day 1.
18. Presence of ocular opacities that, in the opinion of the investigator, preclude imaging and/or reasonable vitreous haze scoring
19. Chronic hypotony (IOP < 6 mmHg) in either eye
20. Ozurdex® (dexamethasone intra-vitreal implant) administered in the study eye during the 6 months prior to Day 1
21. Retisert® (fluocinolone acetonide intravitreal implant) administered to the study eye within the 3 years prior to Day 1.
22. Topical ocular steroid therapy greater than the equivalent of prednisolone acetate 1% every hour while awake within 1 week of Day 1.
23. Uncontrolled glaucoma or ocular hypertension in either eye, defined as an intraocular pressure (IOP) > 30 mmHg while on relevant therapy
24. Ocular surgery in the study eye within the last 4 months except for a diagnostic vitreous or aqueous tap with a small-gauge needle.
25. Laser photocoagulation in the study eye within 3 months prior to Day 1.

No additional exclusions may be applied by the investigator, in order to ensure that the study population will be representative of all eligible patients.

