### 5.5.6.3 Recommended treatment of adverse events

Ocular adverse events should be treated according to the type of adverse event. For clinically significant acute elevation of intraocular pressure (IOP) following LFG316 injection, anterior chamber paracentesis should be performed and normalization of IOP verified. For sub-acute or persistent elevation in IOP, aqueous suppressants may be indicated. Iritis or vitritis should be treated in accordance with permitted medications (see below). Endophthalmitis should be treated with vitreous paracentesis and culture and/or vitrectomy, as indicated, plus appropriate IVT antibiotics per local practice.

**NOTE:** In case of an adverse event attributed to IVT LFG316, the investigator may wish to remove the LFG316 by pars plana vitrectomy.

With any biologic treatment, systemic hypersensitivity reactions are theoretically possible. These can manifest with itching, flushing, headache, nausea/vomiting, hypotension, urticaria, bronchospasm, or angioedema. Assess and treat for anaphylaxis if indicated, and initiate supportive care. Fluids, vasopressors, corticosteroids, antihistamines, bronchodilators, and oxygen should be on hand.

Patients may remain in the study even after receiving treatment for adverse events.

Medication used to treat AEs must be recorded on the Concomitant medications/Significant non-drug therapies eCRF page after the start of study drug.

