### 5.5.7 Concomitant, permitted, and prohibited treatments

Permitted and concomitant therapies are listed in [Table 5-1](#). Concomitant therapies should be entered on the appropriate CRF.

**Table 5-1 Permitted and concomitant therapies** Corporate Confidential Information

Arm:	LFG316 treatment arm	
Eye:	Study eye	Fellow eye
Complement inhibitor (other than LFG316)	Prohibited	Prohibited
Antibody (other than LFG316)	Prohibited	Prohibited
Intraocular surgery	Prohibited	Prohibited
Ocular laser	Prohibited	Prohibited
Systemic steroid or IMT already in use at screening	Permitted up to baseline Will be titrated / stopped per protocol May not be increased in dose or frequency	
New systemic steroids or IMT	Prohibited	
Intravitreal medication (other than LFG316)	Prohibited	Permitted
Periocular/intravitreal steroids	Prohibited	Permitted
New topical steroid or anti-inflammatory	Prohibited	Permitted
Cycloplegic or IOP-lowering eyedrops	Permitted	Permitted
Topical/local anesthetics and antibiotics used for intravitreal administration	Permitted	Permitted
Incidental medications not prohibited above	Permitted	Permitted

IMT = Immuno-Modulatory Therapy

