### 5.5.9 Tapering schedule for oral corticosteroids

If a patient is receiving oral corticosteroids, one of the following schedules will be used for tapering the dose. The selection of the reduction schedule will be based on the prednisone dose the patient was receiving during the week prior to baseline.

1. For patients on up to 100 mg of prednisone-equivalent during the week prior to Day 1, the corticosteroid dose should be tapered according to the following scheme (with the exact doses determined by rounding to the nearest 5 mg): week 1, 85% of the baseline dose; week 2, 67%; week 3, 50%; week 4, 33%; week 5, 17%; week 6, 8%; weeks 7, 0%. Examples of tapering schemes in [Table 5-2](#) are provided for baseline prednisone doses in the range 10 to 100 mg/day. During this schedule, when the patient's prednisone equivalent is 20 mg/day or below, the dose should be taken in the morning after waking up to reduce suppression of the pituitary and adrenal glands.
2. For patients who previously had uveitis that was controlled with a systemic immunosuppressive drug or regimen that was discontinued and whose uveitis has flared and in whom the resumption of prednisone is not considered the appropriate systemic immunosuppressive therapy by the investigator, no prednisone will be given.

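### A topical steroid already in use in the study eye may be increased after Day 1, and a 2-step fall in anterior chamber cells that follows counts as a Day 85 response to LFG316

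*SAP*

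**What the plan says.** **Response.** SAP 7.1 and Protocol 2.1 define Day 85 response by any one study-eye criterion. Among them is "An improvement of 2 or more steps in anterior chamber cells, relative to baseline". None of the response criteria mentions steroid use. Remission, defined in the same sections, requires the patient to be off immunomodulatory therapy, topical therapy included.

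**Entry.** Exclusion 22 in Protocol 4.2 removes only "Topical ocular steroid therapy greater than the equivalent of prednisolone acetate 1% every hour while awake within 1 week of Day 1". Hourly use is therefore allowed. Exclusion 14 asks for three weeks without change in low-molecular-weight immunosuppressants, but "this does not apply to corticosteroid doses".

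**During the study.** For the study eye, Protocol Table 5-1 (Section 5.5.7) prohibits "New topical steroid or anti-inflammatory". The line "May not be increased in dose or frequency" stands in the row for systemic steroid or IMT already in use at screening. The last row permits "Incidental medications not prohibited above". The taper in Section 5.5.9 is for oral drug: "If a patient is receiving oral corticosteroids, one of the following schedules will be used for tapering the dose". Section 5.5.6.3 directs that iritis be treated with the permitted medications.

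**Who decides and who grades.** Under Protocol 5.4 the evaluator is masked and the investigator is not.

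**The concern.** Protocol 3.2 explains that systemic therapy is withdrawn so that the local effect of LFG316 can be seen. A topical steroid in the study eye is also a local treatment, and no visible rule withdraws it, tapers it or holds it steady. An investigator who knows the assignment may raise the drops after Day 1 without breaking a visible rule. If anterior chamber cells then fall by two steps, the primary endpoint records a success for LFG316. Masked grading does not prevent this, because the fall in cells is real; what is in doubt is its cause. The LFG316 arm has 16 patients and the visible test sets its rate against a fixed 60%, so one or two such responders are noticeable.

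**Working it through.** **1. Rules side by side (visible text)**

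| | Systemic steroid or IMT in use | Study-eye topical steroid in use |
|---|---|---|
| Ceiling at entry | none seen | hourly prednisolone acetate 1% or equivalent |
| Stability before Day 1 | 3 weeks for non-steroidal drugs; steroid exempt | none seen |
| Stop or taper | stopped, or tapered under 5.5.9 | none seen |
| No increase | yes, Table 5-1 | none seen |
| New drug | prohibited | prohibited |
| Condition in response | none | none |
| Condition in remission | must be off | must be off |

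**2. How large a fall is needed.** SAP 7.2.1 lists the anterior chamber scores as 0, 0.5, 1, 2, 3, 4 and allows up to 5 steps of improvement. From 4 to 0 there are 5 steps only if 0.5 counts as one. Grade 1 to 0.5 to 0 is therefore 2 steps and qualifies. Grade 0.5 to 0 is 1 step and does not, so only eyes with baseline grade 1 or more can use this route.

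**3. Direction.** Change is measured from the Day 1 pre-dose value, or from screening if that is missing (SAP 7.1). I assume that topical steroid lowers anterior chamber cells.
- Drops stable before and after Day 1: their effect is already in the baseline, so there is no upward push.
- Drops started shortly before Day 1: the baseline may be taken before their full effect, so the bias is upward.
- Drops increased after Day 1: upward.
- Drops reduced after Day 1: cells may rise, so responders may be lost.

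**4. Do the analysis sets catch an increase?** SAP Table 5-2 code M01 covers prohibited medication. Increasing existing drops is not listed as prohibited, and M01 is listed for Efficacy 2 only, while Efficacy 1 is of primary interest. Efficacy 1 stops counting at rescue or discontinuation. The visible rescue rules in Protocol 5.5.6.1 do not name an increase in drops.

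**5. The plan's own figure.** The synopsis gives n = 16, a null rate of 0.60, a 17% false-positive rate and power of 45%, 80% and 92% at true rates of 70%, 80% and 85%. The exact tail is P(X ≥ r) = Σ C(16,k) p^k (1−p)^(16−k), summed from k = r to 16.
- r = 12: 16.7% at p = 0.60; 45.0%, 79.8% and 92.1% at the three alternatives. This matches.
- r = 11, the count as printed: 32.9%; 66.0%, 91.8% and 97.6%. This does not match.

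The mismatch is a separate matter. Here it only explains why 12/16 is the reference count.

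**6. What one patient is worth.** 1/16 = 6.25 percentage points. The 90% Clopper-Pearson limits (the SAP 7.1 method) are the 5% quantile of Beta(x, 17−x) and the 95% quantile of Beta(x+1, 16−x):

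| Responders | Rate | 90% interval |
|---|---|---|
| 12/16 | 75.0% | 51.6 to 91.0% |
| 13/16 | 81.3% | 58.3 to 94.7% |
| 14/16 | 87.5% | 65.6 to 97.7% |

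Two responders who owe their status to increased drops would move the interval from one that contains 60% to one that lies above it.

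**The case against.** Much of the other side's case stands.

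- **Remission is co-primary** (SAP 7.1, Protocol 9.4.1) and requires being off topical therapy. A stricter result is thus reported beside response. It is a different and far more demanding outcome, so it does not show what the response rate would be without increased drops.
- **Response by criterion** is reported for each arm (SAP 7.2.1). The reader will see how many met the anterior chamber criterion, but not which of them had drops increased.
- **A 90% interval for the difference** between arms is planned (Protocol 9.4.1). The comparator's co-medication rules are not visible, so whether the effect cancels cannot be judged.
- **No decision rests on the p-value** (SAP 7.1). That is so, but the rate and its interval carry the same bias.
- **Rescue** covers anterior chamber inflammation that is significantly worse 28 ± 3 days after the last dose and needs other therapy. Some escalations are caught this way; milder or earlier ones need not be.
- **Wording.** A steroid drop for the study disease is hardly incidental, and IMT could be read to include topical therapy, since the remission text groups them. The separate row for new topical steroid makes that reading weak, and no schedule for drops is shown.
- **Redaction.** Table 5-1, the rescue section and SAP 7.5 on supportive analyses are partly or wholly unseen. A rule or an analysis may be there.

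A reader might go further and infer that any study-eye topical steroid can only add responders. The documents do not support that: the endpoint is change from baseline, so stable drops are neutral and reduced drops can work against LFG316.

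**Conclusion.** The gap is real on the visible text and touches the primary endpoint. A patient who follows every visible rule can have study-eye drops increased and be counted as responding to LFG316. The safeguards above limit this but do not remove it.

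The size is unknown and may be zero. To matter, a patient must enter on study-eye topical steroid, have anterior chamber grade 1 or more at baseline, have drops started shortly before Day 1 or increased after it, and meet no other response criterion. Entry requires vitreous haze or chorioretinal lesions, not anterior chamber cells, and the documents give no count of such patients. Each one is 6.25 points of 16. A reader might suppose that a large share of the arm is affected, or that the reported rate is bound to be too high. Nothing in the documents supports either.

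The conclusion assumes that topical steroid lowers anterior chamber cells and that no redacted block governs existing drops. If such a rule exists, that part of the point is already met.

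**What to change.** (a) **Protocol Table 5-1.** Add a row for topical steroid already in use in the study eye: it may continue or be reduced but may not be increased; any increase needed for safety is allowed and recorded.

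(b) **SAP 7.1.** Score as a Day 85 non-responder, kept in the denominator, any patient whose study-eye topical steroid was started or increased after the Day 1 pre-dose assessment. Show the rate under the present definition beside it. Do not label the increase rescue, because Efficacy 1 stops counting a patient at rescue.

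(c) **SAP 8.** Capture the name, strength and drops per day of study-eye topical steroid, as is already asked for systemic steroid doses.

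**Cost.** One table row, one derived flag with a second rate, and one capture item. Concomitant therapies are already recorded and listed by visit, so (c) adds only dose detail. For patients already treated, the flag depends on whether drop frequency was noted.

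**Downside.** A patient who would have responded anyway but had drops increased, for example for iritis after an injection, counts as a failure, so the rate is conservative. The rule is also harsher than the handling of rescued patients, who leave Efficacy 1 at rescue instead of counting as failures. The second rate shows how much this matters. Rule (b) does not reach drops started just before Day 1; the record in (c), read with the concomitant-therapy listing, would show whether there were any.

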## Corporate Confidential Information

**Ocular Assessment schedule**

Corporate Confidential Information

Study phase	Screening Visit	Treatment Period								End of Study (EOS) 	Corporate Confidential Information			
		D-14 to -1	Day 1	Day 2 (+1)	Day 8 (+1)	Day 15 (+/-1)	Day 29 (+/3)	Day 43 (+/3)	Day 57 (+/-3)		PRN	Day 169 (+/-5 days)	PRN	Day 253 (+/-5 days)
Visit Numbers	Visit 1	Visit 2	Visit 3	Visit 4	Visit 5	Visit 6	Visit 7	Visit 8	Visit 9 or 777		Visit 10		Visit 11	
Best corrected visual acuity (ETDRS)	OU 	OU	OU	OU	OU	OU	OU	OU	OU	OU	OU	OU	OU	
Intraocular pressure(IOP)	OU	OU 	OU	OU	OU	OU 	OU	OU 	OU 	OU 	OU 	OU 	OU 	
;;,n lamp oiomicroscopy	OU	OU	OU	OU	OU	OU	OU	OU	OU	OU	OU	OU	OU	
Spectral domain ocular coherence tomography (sd-OCT)	OU	OU				OU		OU	OU		OU		OU	
Dilated ophthalmoscopy	OU	OU 	OU 	OU 	OU	OU 	OU	OU 	OU 	OU 	OU 	OU 	OU 	
Color fundus photo	OU					OU		OU	OU	OU	OU	OU	OU	
Standardized Vitreous Haze Score	OU	OU	OU	OU	OU	OU	OU	OU	OU	OU	OU	OU	OU	
Anterior Chamber cells	OU	OU	OU	OU	OU	OU	OU	OU	OU	OU	OU	OU	OU	
Chorioretinal lesions (absent/present per PI)	OU	OU	OU	OU	OU	OU	OU	OU	OU	OU	OU	OU	OU	
Macular edema due to u iti s (absent/present per PI)	OU	OU	OU	OU	OU	OU	OU	OU	OU	OU	OU	OU	OU	

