## 2 Study objectives

### 2.1 Primary objectives

To assess the effect of intravitreal LFG316 Corporate Confidential Information on the protocol-defined, Day 85 response rate in eyes of patients who meet the inclusion criteria

The above objective applies to the study eye only. A response will be defined by any **one** of the following criteria in the study eye:

- An improvement of 2 or more steps in vitreous haze, relative to baseline. For the purpose of "step" calculation, 0.5 shall count as one of the increments. Thus, improvement from a score of 2 to 0.5 or from 1 to 0 would constitute a 2-step improvement, or
- An improvement of 10 or more letters in visual acuity, relative to baseline, or
- An improvement of 2 or more steps in anterior chamber cells score, relative to baseline or
- Absence of chorioretinal lesions as determined by the investigator
- Change in central retinal thickness from baseline to Day 85 of 50 micrometer

Remission (complete response) will be defined as any patient who has a vitreous haze score of 0 or 0.5 and who has an anterior chamber cell score of 0 and no chorioretinal lesions in the study eye and is off all immune modulatory therapy (systemic, corticosteroids and topical), without any worsening of uveitis during the trial.

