## Corporate Confidential Information

### Corporate Confidential Information

During the screening period (Day -14 to Day -1), eligibility will be verified through applicable ophthalmic/medical history, ocular evaluations, vital signs, safety laboratory tests, electrocardiogram, and pregnancy test.

Ocular assessments include:

- Best corrected visual acuity (ETDRS)
- Intraocular pressure (IOP)
- Slit lamp biomicroscopy
- Dilated ophthalmoscopy
- Standardized vitreous haze score ([Nussenblatt et al 1985](#))
- Color fundus photos
- Spectral domain optical coherence tomography (sd-OCT): Study eye unless otherwise indicated.

- Anterior chamber cells
- Chorioretinal lesions (absent/present per investigator)
- Vasculitis (absent or present per Investigator)
- Presence of chorioretinal infiltrates due to uveitis
- Macular edema due to uveitis (absent or present per Investigator)

If either eye would qualify as the study eye, one eye will be selected as the study eye during the screening period based on the following criteria

- Higher vitreous haze score;
- If not determined by vitreous haze score, then by lower visual acuity;
- If not determined by visual acuity, investigator preference.

At Baseline, vital signs will be checked and compared to eligibility criteria.

Corporate Confidential Information

In preparation of the LFG316 IVT injection, personnel from the study clinic should follow the LFG316 preparation and instruction manuals. These are provided separately. Patients randomized to LFG316, will receive a single IVT dose of LFG316. Postdose safety assessments and ocular examination will occur after the IVT injection. PK/PD blood collection will occur prior to dosing.

Corporate Confidential Information

Patients will return for scheduled follow-up visits (see [Section 3.1](#)), where ocular exams and safety assessments will take place. Safety laboratory studies and ECG will be done at the specified times throughout the trial and at the end-of-study visit.

For assessment details, refer to the [Assessment schedule](#).

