### 4.1 Inclusion criteria

Patients eligible for inclusion in this study must fulfill **all** of the following criteria:

1. Written informed consent must be obtained before any assessment is performed.
2. Male or female patients 18 years or older.
3. Active NIU, in at least one eye, as defined below, in patients requiring intensification of systemic immunosuppressive therapy:
  - Vitreous haze of at least 1+ at screening on the scale of [Nussenblatt et al 1985](#), or
  - Chorioretinal lesions due to uveitis (chorioretinal lesions due to infectious uveitis are excluded)
  - Patients who present with a flare and who are at the time of the emollement on systemic corticosteroid or non-steroidal immunosuppressants will have their therapy tapered or stopped, respectively, at the time of intravitreal LFG316 administration.
4. ETDRS visual acuity of 20 letters (20/400) or better in the study eye.
5. Women of child-bearing potential (WOCBP), defined as all women physiologically capable of becoming pregnant, unless they are using effective methods of contraception during dosing of study treatment and 7 weeks (5 times the terminal half-life) of LFG316.

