### 6.4.3 Chorioretinal lesions

Chorioretinal lesions will be assessed as present or absent by the investigator

Corporate Confidential Information

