## Corporate Confidential Information

However, patients can attend for unscheduled visits as needed and as determined by the investigator. Patients will be monitored for safety and ocular assessments obtained throughout treatment and follow-up periods. Patient eligibility will be assessed as outlined in Figure 2-1 below. An overall study scheme is shown in Figure 2-2 below.

Ocular assessments include:

- Best corrected visual acuity (ETDRS)
- Intraocular pressure (IOP)
- Slit lamp biomicroscopy
- Dilated ophthalmoscopy
- Standardized vitreous haze score (Nussenblatt et al 1985)
- Color fundus photos\*
- Spectral domain optical coherence tomography (sd-OCT)\*
- Anterior chamber cells
- Chorioretinal lesions (absent/present per PI investigator)
- Vasculitis (absent or present per Investigator)

- Presence of chorioretinal infiltrates due to uveitis
- Macular edema due to uveitis (absent or present per Investigator)

\*: sd-OCT images and color fundus photos are only checked for quality and archived.

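### Remission requires a study eye without chorioretinal lesions, but lesions carry no activity status, so a quiet eye whose scar is scored as present is a non-remission

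*SAP*

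**What the plan says.** **How lesions are recorded.** Protocol 6.4.3 states: "Chorioretinal lesions will be assessed as present or absent by the investigator". The ocular assessment schedule has one lesion row, for both eyes at every visit, in the same binary form ("Chorioretinal lesions (absent/present per PI"). The list of ocular assessments in SAP 2.2 repeats it ("Chorioretinal lesions (absent/present per PI investigator"). None of these gives an activity status or mentions scars.

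**Remission.** Protocol 9.4.1 and SAP 7.1 both name remission at Day 85 as primary together with response. Remission is a conjunction: low vitreous haze, no cells, no lesions, no immune-modulating therapy and no worsening. The lesion part applies to a patient "who has an anterior chamber cell score of 0 and no chorioretinal lesions in the study eye". It is not limited to active lesions and not qualified by investigator judgement. The missing-data rules in SAP 7.1 classify a patient as a remission only when every condition is met, and as a non-remission when one is not.

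**Response.** Any one criterion is enough. The lesion criterion reads "Resolution of chorioretinal lesions as determined by the investigator" in SAP 7.1, and the protocol synopsis likewise speaks of resolution. Protocol 2.1 instead reads "Absence of chorioretinal lesions as determined by the investigator". Neither term is defined.

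**Activity elsewhere.** The rescue rule in Protocol 5.5.6.1 refers to active inflammation. Protocol 3.1 and SAP 2.2 also list a separate assessment, "Presence of chorioretinal infiltrates due to uveitis", but it enters neither endpoint.

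**The concern.** Protocol 1.2 gives the purpose as finding out whether LFG316 reduces intraocular inflammation. An inactive scar is what an inflammatory lesion can leave behind once it is controlled. If such a scar is recorded as present, the remission condition fails, and no other finding can make up for it because every condition is required. The endpoint then partly reflects how many eyes carried scars.

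If instead some examiners take the item to mean active lesions only, the same eye is a remission at one site and a non-remission at another. With about 16 patients on LFG316, each such patient moves the remission rate by 1/16 = 6.25 percentage points. Nothing planned later would settle the matter: SAP 2.2 has the OCT images and fundus photographs only quality-checked and archived. The protocol does mention a grading scale for the fundus photographs, but neither endpoint uses a reading from it.

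**Working it through.** The plan gives no figure for remission, lesion prevalence or scar persistence, so there is none to reproduce. The check has two parts.

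**1. Three hypothetical eyes scored by the written rules**

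| Eye | Rule | Scar recorded as present | Item read as active lesions only |
|---|---|---|---|
| A. Old scar; haze 2+ at baseline. At Day 85: haze 0, cells 0, off all therapy, no worsening | Remission | Not met | Met |
| A | Response | Met through haze | Met through haze |
| B. Enters on active lesions with haze 0. At Day 85 the lesions are inactive scars | Lesion response item, *Resolution* | Investigator may judge it met | Met |
| B | Lesion response item, *Absence* | Not met on the literal reading | Met |

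For eye A the haze steps run 2 to 1, 1 to 0.5 and 0.5 to 0. That is three steps against a required two, so it is a responder whatever is decided about the scar. Only its remission status changes.

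Eye B can still respond through acuity or cells, or under the protocol through central retinal thickness (SAP 7.1 omits that criterion).

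Eye C has no lesion at baseline or at Day 85, and its haze, cells and acuity do not change. Under *Resolution* nothing has resolved. Under *Absence*, read literally, the criterion is met and the patient is a responder.

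So the remission problem runs one way: a scar can only turn a remission into a non-remission. The response problem runs both ways: eye B may be lost and eye C may be gained.

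**2. Possible size for remission, by assumption only**

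Let f be the share of study eyes with lesions at baseline, and s the share of those that keep an inactive scar scored as present at Day 85. Neither comes from the documents. With n = 16 on LFG316 (protocol synopsis, sample size):

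- patients who cannot be remissions = 16 × f × s
- ceiling on the remission rate = 1 − f × s

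| f | s = 0.3 | s = 0.5 | s = 0.8 |
|---|---|---|---|
| 0.2 | 0.96 patients, 94% | 1.6 patients, 90% | 2.56 patients, 84% |
| 0.4 | 1.92 patients, 88% | 3.2 patients, 80% | 5.12 patients, 68% |
| 0.6 | 2.88 patients, 82% | 4.8 patients, 70% | 7.68 patients, 52% |

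Example: f = 0.4 and s = 0.5 give 16 × 0.4 × 0.5 = 3.2 patients and 1 − 0.20 = 80%.

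The effect can also be put on the observed rate. If a share u of otherwise remitted eyes keep a scar scored as present, the observed rate is the true rate × (1 − u). A true 50% becomes 45% at u = 10%, 37.5% at u = 25% and 25% at u = 50%.

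**The case against.** The strongest reply is that nothing obliges an examiner to record an inactive scar as a lesion. The call is left to the investigator, who may take it to mean active disease. A reader might infer that a scarred eye can never remit or respond. The documents do not support that: it follows for remission only if the scar is scored as present, and the response item lets the investigator judge a healed lesion resolved. This part of the reply stands and limits the point. It does not remove it, because the remission condition carries no investigator qualifier and the choice between the two readings is written nowhere.

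A reader might also infer that the response rate is pulled down towards the 60% benchmark. That is not established. Any one criterion suffices, the *Absence* wording can add responders, and the basis for the 60% is blacked out, so it may or may not share this lesion definition. SAP 7.1 also says that no decision is to rest on the test against 60%.

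A third inference would be that quiet, scarred eyes can be enrolled on "Chorioretinal lesions due to uveitis (chorioretinal lesions due to infectious uveitis are excluded" alone. Inclusion criterion 3 places that limb under active disease in patients who need intensified systemic therapy, so the entry rule needs no change on this ground.

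Finally, text is blacked out directly after Protocol 6.4.3. The table of contents puts papillitis and vasculitis there, so a lesion-activity rule is unlikely but cannot be excluded. If one exists, the endpoint wording should still match it.

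**Conclusion.** The point holds for remission. The lesion item has no activity status, the condition is unqualified, and one failed condition decides the outcome. An eye with controlled uveitis is therefore a non-remission whenever its inactive scar is recorded as present. As written, this primary endpoint mixes residual scarring with inflammation and leaves room for differences between sites.

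For response the point is smaller: the two documents, and the protocol within itself, use two undefined terms that can classify the same eye differently. The net direction is unknown.

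The size cannot be taken from the documents. Over the assumed ranges (f from 20% to 60%, s from 30% to 80%) the ceiling on remission runs from 94% to 52%. These ceilings apply only on the literal reading in which scars count as lesions.

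**What to change.** - **Protocol 6.4.3 and the eCRF:** record chorioretinal lesions as absent, present-inactive or present-active at each visit where the item is already scheduled.
- **Remission (protocol synopsis, Protocol 2.1, SAP 7.1):** require no active chorioretinal lesions in the study eye.
- **Lesion response item (same places):** use one definition, namely active lesions at baseline with none active and no new lesion at Day 85. This replaces both *Resolution* and *Absence*, and an eye with no lesion at baseline no longer qualifies through this item.
- **Who scores it:** assign the call to the masked examiner who does the eye exams under Protocol 3.1. At present 6.4.3 and the schedule give it to the investigator, who is not masked under Protocol 5.4.
- **Reporting:** keep total presence or absence as a descriptive table.

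The cost is one extra eCRF category at an examination already done at every visit, a written protocol amendment (Protocol 11.1) and matching SAP text. No visit, procedure or reader is added. The drawback is one more clinical judgement, which is why it belongs with the masked examiner. Visits already recorded only as present or absent would lack the activity status unless the source notes supply it.
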